9.8. Discontinuation/Withdrawal of participants from research study

The participants have the right to withdraw from the research study at any time. In addition, the Investigator may discontinue a participant from the research study at any time if the Investigator considers it necessary for any reason including:

- Ineligibility (e.g. if this becomes apparent during the study visit)
- Significant protocol deviation
- Withdrawal of Consent after a blood sample is taken.

Data from participants will continue to be analysed for the study unless the parents/legal guardians or adult participant request this to be withdrawn. Systems are in place to recover stored samples if the participants wish to withdraw their sample.

The reason for withdrawal will be recorded in the CRF.

If for any reason a participant gives consent but either blood is not obtained, or the sample is less than the minimum sample required (as defined by the clinical study plan) then they are not considered a withdrawal. Instead they will be considered as a failed enrolment and will be replaced.

Participants who consent to taking part in the longitudinal cohort will have the option of taking part in up to three additional visits. At each longitudinal visit they will be asked if they would like to opt for another appointment, if they do not wish to do so the CRF will be marked as complete.

9.9. Definition of the end of research study

The end of study will be defined as the completion of data collection.

10. SAFETY REPORTING

10.1. Reporting Procedures for All Adverse Events

Blood and saliva samples are all that is required of participants. No medicinal products will be administered. Given this fact, it is not intended to report non-serious adverse events.

10.2. Reporting Procedures for Serious Adverse Events

Blood and saliva samples and completion of questionnaire is all that is required of participants. No medicinal products will be administered. Given this fact and the scale of the study we will only report serious adverse events that are the result of study procedures.

All SAEs must be reported on the Oxford Vaccine Group SAE reporting form to the Chief Investigator or delegate within 24 hours of the Site Study Team becoming aware of the event. The CI or delegate will perform an initial check of the report, request any additional information, and ensure it is forwarded to the Medical Monitor on a weekly basis. It will also be reviewed at the next Research Study Safety Group meeting. Additional and further requested information (follow-up or corrections to the original case) will be detailed on a new SAE Report Form and emailed to CTRG.

The principal Investigator's opinion will be used to determine if the event was 'related' (resulted from administration of any of the research procedures) and/or 'unexpected' in relation to those procedures. Reports of related and unexpected SAEs will be submitted to the ethics committee within 15 working days of the Principal Investigator becoming aware of the event, using the NRES report of serious adverse event form (see IRAS/NRES website).

10.3. Criteria for the Termination of the Study

The study does not involve the administration of any medications to participants. It is therefore unlikely that any safety issues would lead to termination of the study.

The investigator has the right to discontinue this study at any time. Recruitment will stop immediately if the study is prematurely terminated.

11. STATISTICS AND ANALYSIS

11.1. Description of the Statistical Methods

A detailed statistical analysis plan will be produced prior to receipt of the data by the Statistician.

Data analysis will include:

Primary Objectives and Outcomes

 Representativeness assessment by comparison to census or other population data on sex, ethnicity, community membership, migrant population, socioeconomic background, vaccination uptake (from PHE Cover data). At a site level representativeness will be to local census data and/or according to characteristics of those who respond to those who do not. Overall representativeness will be compared to national data. This will be done descriptively, and differences assessed by Chi-squared or Fisher's exact test and multivariable methods as appropriate to adjust for the age distribution.

 A comparison of the proportions protected against diphtheria and Men C using residual and prospectively collected samples. This will be done overall and within broad age groups (see sample size section) with adjustment in a logistic regression analysis for confounding factors such as finer age groups and, if necessary sex and region.

Secondary Objectives and Outcomes

- Description of recruitment rates (participants recruited per month) and cost per sample obtained. This will be done overall, by site and by method of survey.
- Description of response rates (proportion invited that respond and the proportion that respond that are recruited and bled). This will be overall and by site and survey method as well as by age group. Proportions will be calculated with 95% confidence intervals. A more detailed analysis of response rates will be done by post-code and other demographics collected from the nonresponse survey.
- For prospectively collected samples where vaccination history is known in children aged between 3 and 14 years, the proportion of individuals within each age band that have antibodies to diphtheria antitoxin ≥0.01IU/mL and antibodies to diphtheria antitoxin ≥0. 1IU/mL, and whether levels of diphtheria anti-toxin are associated with the brand of diphtheria pre-school booster administered. Trends by age and differences by vaccination status will be assessed by Chi-squared of Fisher's exact test as well as by using logistic regression. Comparisons by geometric mean titres will also be done by t-tests or Kruskal Wallis as appropriate and by plotting geometric means with 95% confidence intervals by age groups.
- For prospectively collected samples where vaccination history is known, in individuals aged 12 -24 years, the proportion of individuals within each age band that have serum bactericidal titres of ≥8 to group C meningococcal disease, and whether SBA titres are associated with adolescent Men ACWY or MCC vaccine or not having received vaccine. Trends by age and differences by vaccination status will be assessed by Chi-squared of Fisher's exact test as well as by using logistic regression. Comparisons by geometric mean titres will also be done by t-tests or Kruskal Wallis as appropriate and by plotting geometric means with 95% confidence intervals by age groups.
- Across the whole age range (0-24 years) a comparison of proportions protected with previous seroprevalence studies carried out in 2009 and 1996 for diphtheria and 1996-99, 2002-4, 2009 and 2014 for Men C. This will be done by using all the samples and calculating prevalence within individual age bands with 95% confidence intervals and inferring differences based on non-overlapping 95% CIs which is conservative to allow for multiple testing when assessing many age bands.
- For all participants, a repeat cross-sectional analysis of the geometric mean titres (with 95% CI) of antibodies against SARS-CoV-2, and proportion (with 95% CI) of participants with anti SARS-CoV-2 antibodies above a (yet to be determined) threshold of 'positivity' throughout the study period
- For participants providing multiple serum samples, analysis of the proportion of participants who were initially seronegative who subsequently developed antibodies against SARS -CoV-2
- For participants providing multiple serum samples, analysis of the kinetics of the rise and fall of antibodies against SARS -CoV-2
- Calculation of the sensitivity and specificity of salivary antibody testing compared to serum.

Exploratory analyses

- Whether ethnicity, household income or other factors collected on the questionnaire are associated with antibodies against diphtheria and / or Men C and/or SARS-CoV-2. This will be done by multivariable logistic regression.
- Comparisons between groups 1 and 2 will be performed as detailed in study statistical analysis plan in terms of:
 - representativeness of ethnicity, community identity, migrant population and socioeconomic background of local communities
 - immunological end-points
- Comparisons in the immunological end points will be performed as detailed in study statistical analysis plan between samples collected in this study and those obtained from testing of residual samples through the existing PHE seroepidemiology unit

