6. OBJECTIVES AND OUTCOME MEASURES

	Objectives	Outcome Measures
Primary	 To evaluate the feasibility and added public health benefit of an England, population based sero - epidemiological programme in 0 to 24 year olds 	 Representativeness of participants sampled, in terms of the local population's ethnicity, community identity, migrant population and socioeconomic background Comparison with serological markers of immunity for vaccine preventable diseases as measured in an age matched cohort in current residual sera programme
Secondary	 To evaluate the effectiveness of recruitment methods employed To assess, in relevant age groups, antibody concentrations against infections and vaccine preventable diseases including, but not limited to diphtheria, group C meningococcus and novel coronavirus (COVID-19) 	 Recruitment rate per month, recruitment rates as percentage of potential participants contacted, cost per sample obtained disease specific correlates of protection/markers of immunity, e.g. : Anti-Diphtheria Toxoid IgG concentrations Capsular Group C meningococcal Serum bactericidal activity (SBA) titres Serum IgG to SARS-CoV-2 antigens, including spike protein and/or nucleocapsid (as measured by ELISA and/or neutralising assay)
	• To develop a store of sera from a representative section of 0 to 24 year olds available for future testing of immunity against other infectious diseases of relevance to UK immunisation schedule and public health.	• A collection of anonymised sera from participants with appropriate consent and known demographic details and immunisation history'
	 To determine the prevalence of SARS- CoV-2 infections in 0 – 24 year olds, and variation in prevalence in time, age, ethnicity and geography (cross- sectional sero-epidemiological study) 	 Serum IgG to SARS-CoV-2 antigens, including spike protein and/ or nucleocapsid (as measured by ELISA and/or neutralising assay)

	 To determine the kinetics of antibodies specific to SARS-CoV-2 following infection in a paediatric population (serial blood sampling in population sub-group) To determine relationship between serum and salivary antibodies against SARS-CoV-2 	 Serum IgG to SARS-CoV-2 antigens, including spike protein and/or nucleocapsid (as measured by ELISA and/or neutralising assay) Salivary IgG to SARS-CoV-2 antigens, including spike protein and/or nucleocapsid (as measured by ELISA)

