9. PROTOCOL PROCEDURES

9.1. Recruitment Group 1

The recruitment plan below aims to recruit a representative sample of the region. Potential participants will be contacted by mailing out invitation letters with study information booklets to the parents/legal guardians of age appropriate children via the NHS England Databases, the Child Health Information Service or through the Clinical Research Network. There may also be other promotion such as website based advertising, social media, radio, printed publications, contacting families registered with a study site research database and poster advertisements. Potential participants can also be identified by the local study team through their visits for other research studies. Dissemination of the study information, including through GP practices and with health visitors may also be employed. The participant information will be available on websites if available and recruitment material can direct potential participants to this. Participants interested in taking part will contact sites to arrange visits. In the first stage recruitment will be capped (e.g. at 10 per age group per region) to allow for corrections if the initial sample is not representative of the region.

We are aiming to ensure that the sample is broadly representative of the region according to IMD (Index of multiple deprivation scores). Other details collected in the questionnaire such as ethnicity, community identity and FASiii are for later analysis.

We are mailing out using NHS England Databases with the expectation that 5-10% of those contacted will respond.

Recruitment plan

- 1. PHE will be generating a list of all postcodes in recruiting regions and determining the quintiles of IMD (index of multiple deprivation scores) within that region.
- 2. All sites to email us postcodes in their catchment areas (i.e. areas from which they can recruit). They will also indicate whether they are rural or urban areas. There is a recognition that there is no formal definition of these terms, and many post codes will be mixed, but this is an area where local knowledge could be applied.
- For each region (i.e. Bristol, Yorkshire and Humber, Southampton etc.) PHE will randomly select 5-7 postcode districts stratified to match the ratio of rural to urban postcode districts to the region's urban/rural population distribution. A postcode district is the first two letters and number e.g.

OX	3	7	LE
Area	District	Sector	Unit

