- 4. Mail outs will be conducted either through NHS England Databases (coordinated by OVG) or through local Child Health Information Services (CHIS).
- 5. In order to maintain even recruitment across time, age and postcode, recruitment numbers will be managed as per section 7.1 (study design).
- 6. It will be made clear in the participant information that participants (and/or their families) may not hear from us immediately, as the aim is to achieve a representative sample for that region. Therefore, every participant that contacts us from the first mail out can go into a study database containing basic contact details and age. This can be searched to see if any of the participants are from quintiles that are under-represented in the sample.

[figure not shown]
Timings of mail outs will be adjusted for sites dependent on their own local recruitment rates.

Those parents/legal guardians that indicate that they do not want to take part in the study and/or receive further communication about the study will not be included in any subsequent contact lists.

For non-responders, postcode and therefore deprivation level (according to Index of Multiple Deprivation) could potentially be estimated. Alternatively, a non-responder questionnaire, with basic demographic details could be administered by mail as per the Dutch study, enabling an assessment of potential bias due to non-response.

9.2. Recruitment Group 2

For the sites recruiting to Group 1, enrolment to group 2 will primarily be by re-allocation of participants from Group 1, as shown in figure 3.

Recruitment in sites only recruiting to group 2 will be carried out using various recruiting procedures, such as generalised mail outs, press releases, radio, social media adverts, schools or community clinics, dissemination of the study information through GP practices and identification of potential participants by the local study team, staff communication channels and inpatients or outpatients clinics as long as potential participants are not patients.

9.3. Group 3

Recruitment will be by multiple approaches, including mail outs and advertising in community (e.g. community centres, religious establishments,) or GP practices and Pharmacies where we have ethics approval for them to act as PICs. These can vary according to each site's experience and their contacts within their local community on how is best to approach the BAME community. Individuals will be directed

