		significance, assuming		significance, assuming	
		population much larger		population much larger	
		than sample (>=10 fold))		than sample (>=10 fold))	
5%	3.0-7.7	2.3,9.1	4.1-6.0	3.8,6.5	
10%	7.2-13.5	6.0,15.3	8.8-11.3	8.2,12.0	
15%	11.6-19.0	10.0,21.0	13.6-16.5	12.9,17.3	
20%	16.1-24.4	14.3,26.6	18.4-21.7	17.6,22.5	
25%	20.7-29.7	18.8,32.0	23.2-26.8	22.4,27.7	
30%	25.5-34.9	23.3,37.3	28.1-31.9	27.2,32.9	

Table 3: Assessment of representativeness, precision and detectable differences

Comparison with residual samples

For comparison with the residual samples this is considered within age strata and is based on the 2017 data on residual samples for the numbers of residual strata by age. Due to the smaller number of residual samples in younger age groups (one of the key reasons for undertaking a community based seroprevelance survey), detectable differences are relatively large in those <4 years. In older age groups relatively, small differences can be detected in >4 year age bands. The example given below is for when the observed prevalence is 50% is the survey which is conservative as this gives the largest detectable differences.

Table 4: Comparison to residual samples by age strata with a total sample size of 2300

Age	Detectable difference from 50% (80% power, 5% significance)
<4	10.7
4 to 8	8.7
9 to 13	8.1
14 to 24	5.7
All Age	3.9

11.2.2: Group 1 and 2 combined

Sample size for SARS-COV-2 incidence based on change in prevalence

Across group 1 and 2 combined there will be over 3500 blood samples from 2800 to 3500 participants in total, at least 3200 of which will be from participants 19 years of age or younger. The intent of this is to obtain blood samples across 4 age bands (i.e. 100 in each of 0 -4 years, 5-9 years, 10-14 years, 15-19 years)to the end of the study. This will include sample taken from the longitudinal cohort, with seroprevalence calculations taking into account over-sampling of participants with positive SARS-Cov 2 antibodies at V1.

The table below shows the precision (95% CI) of estimates of change in prevalence (incidence) with 100 samples at each of two time points. For example with a prevalence of 10% at baseline and 30% at the next time point the incidence is 20% with 95% CI 9.3-30.7. The aim is to achieve 100 in each of 4 age groups at each time point.

Prevalence				
At next time				11.3. Analysis
point	0%	10%	20%	populations
10%	10 (4.1, 15.9)			 The analysis population for recruitment rates will be all

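### Conversion is defined as responders bled over all responders, so where a recruitment quota is full it partly measures the quota and not willingness

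*Protocol*

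**What the plan says.** Section 6 lists the outcomes for the secondary objective on recruitment methods: "Recruitment rate per month, recruitment rates as percentage of potential participants contacted, cost per sample obtained". Section 11.1 reports recruits per month and cost per sample ("This will be done overall, by site and by method of survey"). It then describes response as the "proportion invited that respond and the proportion that respond that are recruited and bled", with this breakdown: "This will be overall and by site and survey method as well as by age group". Section 11.3 fixes the denominator: "The analysis population for recruitment rates will be all" those who were invited.

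Other sections control the numbers being measured:

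- Section 9.1 says "In the first stage recruitment will be capped (e.g. at 10 per age group per region", to leave room for correction if the sample proves unrepresentative.
- The recruitment plan in 9.1 keeps numbers even over time, age and postcode, and adjusts the timing of mail-outs to each site's recruitment.
- Volunteers are told that they "may not hear from us immediately, as the aim is to achieve a representative sample for that region". Responders to the first mail-out can be entered in a database, which can be searched for under-represented deprivation quintiles.
- The lay summary foresees a steady monthly flow of samples, and section 5 sets a goal of 400 participants per month through 2020.

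Letters are the main route into Group 1, but not the only one: "There may also be other promotion such as website based advertising, social media, radio". Research databases and visits for other studies are also named.

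**The concern.** The conversion ratio has every responder in its denominator, but its numerator cannot exceed the number of places. Three kinds of responder are counted alike as not bled: those who declined, those whose blood could not be taken, and those who were willing but not called because their age group, region or quintile was full. Only the first two say anything about how well recruitment works.

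Where places run out, a better response lowers the reported conversion. The comparison by age is exposed in particular, because the overflow group is open only up to age 19. Someone planning a later survey from these figures could take a popular cell for one with poor uptake. Recruits per month has a milder form of the same problem, since the plan paces it.

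**Working it through.** **Inputs from the protocol.** Group 1 total 2300 and up to about 383 per region (11.2.1). One-year bands to age 21 plus one band for 22-24, with 100 per band (11.2.1). First-stage cap of, for example, 10 per age group per region (9.1). Expected response to mail-outs 5-10% (9.1). Group 2 up to 1200 people aged 0-19 (section 2).

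**Assumed, because the documents give no figure.** Number of responders per cell, number of letters per region, share of responders who would be bled if offered a visit, and an even spread of responders over age bands.

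**1. The plan's own figures.** 22 one-year bands + 1 = 23 bands; 23 × 100 = 2300. 2300/6 = 383.3, so the regional figure corresponds to six regions. The protocol gives no target or computed value for the recruitment rates themselves.

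**2. Places per cell.** 383/23 = 16.7, about 17.

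**3. Reported conversion at the full Group 1 allocation.** With r responders, a proportion p who would be bled if offered, and q places:

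reported conversion = min(q, p × r) / r

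With p = 100% and q = 16.7:

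| Responders in cell | Bled | Reported conversion |
|---|---|---|
| 10 | 10 | 100% |
| 25 | 16.7 | 67% |
| 50 | 16.7 | 33% |

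Everyone offered a visit is bled in all three rows. Only the number of volunteers differs.

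**4. First stage, one region.** Cap 10 × 23 = 230 places; 10,000 letters assumed.

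| Response | Responders | p | Willing | Bled | Bled/responders | Bled/letters |
|---|---|---|---|---|---|---|
| 5% | 500 | 60% | 300 | 230 | 46% | 2.3% |
| 5% | 500 | 90% | 450 | 230 | 46% | 2.3% |
| 10% | 1000 | 60% | 600 | 230 | 23% | 2.3% |
| 10% | 1000 | 90% | 900 | 230 | 23% | 2.3% |

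With the cap binding, conversion does not distinguish 60% from 90% willingness, and it halves when response doubles. Bled over letters is the same in all four rows. Bled over responders *offered a visit* would be 60% or 90%, as it should be.

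**5. Cap not binding.** With 2,000 letters at 5% there are 100 responders, and 60 or 90 are bled. Conversion is then 60% or 90%, the true willingness.

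**6. Response among the invited.** Responders/invited is 5% or 10% in every row above. It is settled before any cap applies.

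**7. Comparison by age.** Take 25 willing responders in each of two one-year cells. The surplus over Group 1 places is 25 − 16.7 = 8.3. At age 10 the surplus can move to Group 2. If all 1200 places went to the six Group 1 regions, there would be 1200/20/6 = 10 per one-year cell, enough to absorb it, and conversion would read up to 100%. (Additional sites take some of these places, so 10 is an upper limit.) At age 20 there is no Group 2, and conversion reads 67%. Willingness is identical in the two cells.

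**The case against.** Much can be said for the plan as written.

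- **The cap of 10 is temporary and an example.** This stands, so the main figure above uses the full allocation of about 17 places. Overflow into Group 2 also absorbs surplus, but only at ages 0-19.
- **Holding is not refusal.** A reader might infer that volunteers are called only if their stratum is short. Section 9.1 does not say so. It describes possible delay and a database that can be searched. How many willing people are never called is unknown.
- **Advertised recruits.** A reader might infer that people who came by radio or social media inflate the mail-out response rate. The wording of 11.1 and 11.3 does not support this: the numerator is drawn from those invited, so an uninvited volunteer is in neither count. Section 11.1 also splits rates by site and survey method. What remains is narrow. Section 6 speaks of people contacted, an overall figure is planned, and the protocol does not equate survey method with route of entry.
- **Importance.** A reader might treat these rates as the primary evidence on feasibility. In section 6 the primary outcomes are representativeness and the comparison with residual sera. The recruitment rates are descriptive secondary outcomes with no success threshold.
- **Failed venepuncture.** Sections 9.5 and 9.8 already treat it as a failed enrolment that does not count as recruited, so the numerator needs no repair.
- **Detail for the analysis plan.** Operational detail may be left there. But 11.1 does state what conversion is, and that stated ratio has the wrong denominator for a capped design. An analysis plan also cannot recover an offer status that nobody recorded.

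**Conclusion.** The point holds for conversion and, in part, for recruits per month, and only where a quota binds. With about 17 places and an assumed 25 willing responders per cell, conversion reads about 67% when the true figure is 100%. The size depends on the number of responders per cell, which the documents do not give: there is no distortion while places remain, and it grows as volunteers increase. Since 383 is given as an upper figure per region, fewer places would lower the ratio further. Comparison of conversion by age is affected because overflow stops at age 19.

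The proportion of invited people who respond is sound. The broader conclusion that the recruitment outcomes do not measure how well recruitment works is not supported. This is a worthwhile, inexpensive correction to a descriptive secondary outcome, and the serological analyses are not touched.

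**What to change.** In section 11.1:

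1. Define conversion as participants bled divided by responders offered a visit.
2. Report responders not called because a quota was full as a separate category from those who declined or were not bled, overall and by age group and site.
3. Report eligible responders per month, including those held, beside recruits per month.
4. State that every rate with an invited denominator, including the percentage of people contacted in section 6, covers only individually invited people. Give advertised and other uninvited routes as counts and cost per sample.

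The cost is a change of wording plus two items per responder: whether a visit was offered, and the route of contact. Planned recruitment runs to June 2021, so new fields may come too late for most participants. The items would then have to be retrieved from mailing and contact records. Where they cannot be traced, the report should say so and give the number untraced.
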